The primary aim is to determine the efficacy of training with this exoskeleton and its ability to improve transfers to standing and sitting as assessed by the five times sit-to-stand test. A secondary aim will be to assess effects of the device during overground ambulation. Outcome measurements to investigate changes of knee range of motion and loading of the paretic limb will be accomplished using an instrumented goniometer; changes in limb loading will be monitored using a foot pressure mapping system; and stepping parameters will be recorded using the GaitRite carpet. An exploratory outcome of changes in energy expenditure during ambulation with and without the powered exoskeleton will be assessed from a 6-minute walking test using a portable metabolic cart. Another exploratory outcome measures of QOL will be determined using the SF-36 and

the Stroke Specific Quality of Life Scale. Additional exploratory outcomes to measure body composition, bone mineral density changes will be assessed using Dual X-ray Absorptiometry (DXA). Additional exploratory outcomes include measuring changes in cortical, corticospinal and spinal excitability in response to brain, spinal and peripheral nerve stimulation (PNS), and brain activation using electroencephalogram (EEG).

Baseline testing for both groups will be performed while ambulating without the device and prior to starting in the training program. The exoskeleton group will repeat testing within the first 3 sessions of the training program. Mid-point assessments will be obtained after 12 and 24 sessions of training. Post assessments will be obtained after 36 sessions of training. Retention will be assessed by repeating the assessments without the exoskeleton after 1 month of stopping the training program.

It is anticipated that longitudinal training with the device will increase number of squats achievable, increase knee flexion during swing, increase loading of the paretic limb, and induce symmetrical stepping. No immediate effect on energy expenditure by the device is expected however, a training effect is expected to demonstrate improvement in the energy cost of ambulation. Any gains observed during this study may not be retained, but as this device has the potential to be used in the home and community environment, justifying a prescription of this device for retention purposes may be warranted. Use of this device may also lead to improvement of QOL.

2. Specific Aims

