During ambulation, stroke survivors reduce loading of the paretic lower extremity (LE) by decreasing the amount of weight and time spent loading the limb (1). Alterations in gait combined with general decreased activity are associated with reduced muscle strength of the paretic LE (4). The combination of LE weakness and altered gait can lead to cardiovascular deconditioning and reduced QOL. In effort to increase mobility to a greater extent than that of ambulation with use of typical passive orthotics, powered exoskeletons are being developed to enhance or enable persons with stroke to ambulate thus promoting the use of their paretic limb. These powered devices use motors that power joint rotation to assist the stepping action during ambulation. Learning to ambulate independently in these devices is difficult and lengthy (5, 6). A new powered orthotic exoskeleton, which powers only the knee joint by monitoring volitional movement of the hip joint offers a simple and intuitive approach to assist with ambulation. The range of motion (ROM) of the knee can be adjusted to assist with knee flexion during the swing phase and knee extension during the stance phase of gait. The level of assistance and intuitive activation of this device is hypothesized to promote greater use of the paretic limb in persons with stroke.

The purpose of this pilot project is to investigate the use of a powered orthotic exoskeleton that provides active assistance to the knee joint in persons with impaired gait due to stroke. This pilot project will assess the changes in use of the paretic LE, energy expenditure of walking with and without the powered orthotic exoskeleton, measure longitudinal changes in QOL, bone density, body composition, neuronal excitability, and brain activation. Promoting greater use of the paretic limb in stroke survivors is expected to improve the energy cost of walking and QOL. The results of this work are anticipated to power future investigations of using powered orthotic exoskeletons in the home and community environments to improve ambulatory ability, functional capacity, and thus further improve QOL. The potential for associated benefits for improved cardiovascular function will also be explored in future studies.

Primary Aim: To determine the change in the ability to squat (LE power) as measured by the Five Times Sit to Stand Test (5xSTS), while wearing and not wearing the powered exoskeleton.

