The 5xSTS is used to determine leg power and an aspect of transfer skill. This test will be used to assess a level of improved function while wearing the device. It will also be used to determine if any training effect is observed after 3 months (36 sessions) of training when not wearing the device.

Secondary Aim: To determine the efficacy of ambulation training using a powered orthotic exoskeleton on knee ROM and loading of the paretic LE while ambulating over ground with and without the device for 3 months (36 sessions).

Multiple outcome measures will be used to determine the effect of the powered exoskeleton on a person's gait biomechanics and functional competency. An instrumented goniometer will record knee joint angles during multiple gait cycles to assess changes in knee flexion during the swing phase. Because the powered orthotic exoskeleton provides stability during the stance phase, stepping parameters will be assessed using an instrumented carpet to determine if the paretic limb has more equitable and symmetrical load.

Secondary Aim: To determine the energy expenditure of ambulation with and without the powered orthotic exoskeleton at baseline and 3 months (36 sessions) post training.

A portable metabolic cart will assess oxygen consumption during the two ambulation conditions (i.e., with and without the device) over a 6-minute period. It is anticipated that the baseline comparison test will not show any metabolic changes due to the added weight of the device and negate any metabolic benefit from the motors powering the knee joint movement. However, a training effect over the 3 months (36 sessions) compared to baseline is anticipated due to the participant becoming more comfortable with the device, thus using the paretic LE more effectively.

Exploratory Aim: To determine the retained function (squatting, knee ROM, paretic LE loading and energy expenditure) 1-month post cessation of training without the device.

It is not known whether any benefits from training will be retained, but if benefits exist while wearing the device, but are not retained, then long term use may be indicated.

Exploratory Aim: To determine differences in QOL measurements (SF36 and Stroke Specific Quality of Life Scale [SS-QOL]) over 3 months (36 sessions).

The mobility portions of the SSQOL and SF36 will be used to determine whether changes in ambulation affect QOL in persons post stroke.

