This device separates itself from the other powered exoskeleton devices (e.g., Indego, Ekso) because it only provides assistance to the knee joint and requires the user to have some ability to ambulate independent of the device. Therefore, the user must be able to initiate the active movement, which will then be enhanced by assistance from the Keeogo. The system assists the knee to enhance user-initiated movements by using kinetic and kinematic data from sensors located at the knee and hip joints to assist in all phases of the gait cycle, i.e. knee flexion and extension in swing phase, knee extension (both eccentric control and concentric assist) in stance phase. In addition to gait, the device assists during other functional lower extremity activities, i.e. squatting motions, kneeling, walking, stair climbing and stand-sit/sit-stand transfers. Keeogo™ has two essential functions: (1) to provide kinematic amplification during the swing phase of gait and (2) to provide stability for the stance phase of gait through knee bracing coupled with non-linear spring-like assistance. Keeogo™ is designed to operate intuitively through automatic sensing and augmenting the user's natural walking movement. The eccentric control assists during the gait cycle at initial contact (loading response), squat (Figure 5), kneel, stand to sit and stairs. The eccentric control applies the torque gradually, thus stabilizing the knee and preventing buckling.

Figure 5: Squatting in the Keeogo

Outcome Measurements and Testing sessions: The timeline for conducting testing sessions is outlined in Table 2. Screening participants and obtaining their medical history and demographics will be obtained once, prior to initiating training. Baseline assessments that do not involve the exoskeleton will be obtained prior to training in both groups. Baseline assessments, which involve the exoskeleton (for the exoskeleton group only) will be obtained during the first three sessions after the participant has been correctly fitted and acclimated to the exoskeleton. Testing will be repeated after training session 36 (3 months) without the exoskeleton for both groups and repeated with the exoskeleton for the exoskeleton group. All participants (control and experimental) will be asked to return 1-month post cessation of training for a follow-up visit where all the outcome measures will be repeated without the exoskeleton for both groups (Table 2) to assess retention of functional gains.

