The 5xSTS test will be used to address the primary aim of improving participants' squatting ability (LE Strength) (33). This test is performed using a standard free-standing chair with a straight back, solid seat and a seat height of 17 inches. Participants will be instructed with the following statement "By the count of 3, please stand up and sit down as quickly as possible for 5 times. Place your hands on your lap and do not use them throughout the procedure. Lean your back against the chair's backrest at the end of every repetition." The time to complete the test will be recorded and will start once the person back leaves the back rest and stops once the back touches the back rest for the 5th time.

Assessment of gait changes will be performed using the GaitRite Carpet (CIR Systems Inc), the F-scan foot pressure system (Tekscan) and the instrumented goniometer (bendlabs). These measurements will be performed with and without the device. The GaitRite measurement will be obtained by asking each participant to walk over a carpet equipped with sensors, which provide information regarding cadence, step length and time spent on each foot. The F-Scan foot pressure system requires the participant to walk with a disposable insole, which is cut to fit inside their shoe. The disposable insole contains an array of sensors, which provide a continuous pressure profile of each foot during ambulation. This system will measure the percentage of total body weight loaded during the different segments of the stance phase (heel-strike, stance and toe-off) as well as Protocol ASS-20-01

MIRB# 01929

Table 2: Timeline for testing and training

Week:	Schedule of Procedures and Testing									
	-2 to -1	-1	1-4	4-5	5-8	8-9	9-12	12-13	16	
Phase	Pre Screen	Screening /Baseline Testing	Training	Assessments	Training	Assessments	Training	Post Assessments	1-Month Follow-up	
Chart reviews	x									
Consent	x									
Medical History/ Demographics		x								
Fugl-Meyer		x		x		x		x		x
EEG	x		x					x		x
Neuronal Excitability		x						x		x
DXA	x							x		
QOL(SF36 and SSQOL)		x						x		
Training session number			1-3	3-12		12-24		24-36		
Assessments with out Keeogo (both Control and Exoskeleton group)										
5xSTS	x	d	d	x	d	x	d	x		x
Gaitrite	x	w	w	x	w	x	w	x		x
F-Scan	x			x		x		x		x
Energy Expenditure	x			x		x		x		x
Knee range while walking	x	w	w	x	w	x	w	x		x
10mWT	x	d	d	x	d	x	d	x		x
TUG	x	w	w	x	w	x	w	x		x
6MWT	x	d	d	x	d	x	d	x		x
Assessments with Keeogo (only Exoskeleton Group)										

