The loading profile obtained from the F-Scan foot pressure system will be normalized over the gait cycle as percentage of gait cycle and percentage of body weight for each foot. The total area under the curve will be calculated to obtain a total load on each lower extremity. Peak measurements from heel strike and toe-off will be calculated from the curve along with mid stance where load is typically diminished. Maximum knee flexion angles from 10 continuous steps will be averaged for each limb.

Metabolic measurements (VO_2 , HR and RR) will be recorded as averages every minute. Energy cost of distance travelled will be calculated by dividing VO_2 normalized to body weight (ml/kg/min) by the distance traveled (ml/kg/m). The 6 values from the consecutive 1-minute recordings will be averaged for sitting and walking conditions.

Descriptive statistics will be employed for demographic and Fugl-Meyer data. A single group, repeated measures design will be employed in the experimental group to test the within-group effect of using the powered exoskeleton. A two group repeated measures design will be employed to test the between-group differences in outcomes. All outcome measurements will be analyzed using a mixed model ANOVA to determine significant main and interaction effects of group (control, experimental) and time (baseline, session 36, 1-month follow-up). A similar mixed model ANOVA will be used to determine significant main and interaction effects of the two conditions (without [w/o] and with [W] Keeogo exoskeleton) in the experimental group for the 3 time points (baseline, session 36, 1-month follow-up). Post hoc analyses of significant data will be performed using t-tests.

Table 3: Timeline of activities to complete the study

TIME LINE	Year 1				Year 2			
	Q1	Q2	Q3	Q4	Q1	Q2	Q3	Q4
Start-up Activities								
IRB & R&D	x				x			x
Staff Hiring and Training	x							
Purchase Equipment	x							
Database development	x							
Participant Screening	x	x	x	x	x	x		
Participant Enrollment	3	4	4	3	1	0		
Database management	x	x	x	x	x	x		
Abstract writing				x	x	x		
Manuscript writing					x	x		

Potential Difficulties and Limitations

The greatest hurdle in conducting investigations with devices is recruiting participants and completing the training as well as obtaining regulatory approval to conduct the study. Feasibility to enroll and complete the 15 participants is

Protocol ASS-20-01

MIRB# 01929

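### The baseline with- versus without-device contrast compares a pre-training test with one taken in sessions 1–3, so it is confounded with practice and early training; test order at later assessments is unspecified

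*Combined protocol and SAP*

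**What the plan says.** Under Outcome Measurements and Testing sessions, the protocol sets two baseline times. For tests without the device: "Baseline assessments that do not involve the exoskeleton will be obtained prior to training in both groups". Tests with the device, in the exoskeleton group only, "will be obtained during the first three sessions after the participant has been correctly fitted and acclimated to the exoskeleton". The opening summary, ahead of Section 2, agrees: "The exoskeleton group will repeat testing within the first 3 sessions of the training program".

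For the end of training: "Testing will be repeated after training session 36 (3 months) without the exoskeleton for both groups and repeated with the exoskeleton for the exoskeleton group". For the gait measures: "These measurements will be performed with and without the device". Neither sentence gives the order of the two conditions, the rest between them, or whether testing comes before or after that day's training.

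The aims use this contrast. The primary aim concerns the 5xSTS "while wearing and not wearing the powered exoskeleton". One secondary aim in Section 2 is "To determine the energy expenditure of ambulation with and without the powered orthotic exoskeleton at baseline and 3 months (36 sessions) post training".

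Description of Data and Statistical Analyses plans a mixed-model ANOVA for "significant main and interaction effects of the two conditions (without [w/o] and with [W] Keeogo exoskeleton) in the experimental group", over baseline, session 36 and the 1-month follow-up. It has no term for order, session or period. Control participants are not in this model.

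**The concern.** The test without the device always comes first, before any training. The test with the device always comes later, after fitting, acclimation and possibly some training and repeat testing. According to Description of Training Sessions, training includes walking and chair rises, which are the tasks being tested. A participant who improves simply by having done these tasks a few more times will show a difference between the two baseline tests even if the device does nothing. The model would read that difference as the effect of the device.

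Two conclusions are at stake: the immediate effect of wearing the device, and whether that effect changes with training (the condition-by-time interaction). Section 2 also predicts no metabolic difference at baseline, and a contrast split in time cannot test that cleanly. The protocol expects its results to inform the power of later studies, so a biased device effect would carry forward.

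**Working it through.** The plan gives no alpha, SD, effect size or power for the device contrast, so there is no figure to reproduce. The check covers timing, what the contrast estimates, and an illustration on assumed values.

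**1. Exposure between the two baseline tests.** The with-device test falls during sessions 1–3, so at most two full sessions and part of a third precede it. At the ceiling, 3/36 = 8.3% of the training; counting full sessions only, 2/36 = 5.6%.

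**2. What the contrasts estimate.** Let D0 and D36 be the true device effects at baseline and session 36. Let b be the shift from practice and early training between the two baseline tests, and o any order effect at session 36.
- Baseline contrast = D0 + b.
- Session-36 contrast = D36 + o.
- Interaction (session 36 minus baseline) = (D36 − D0) + (o − b).
- Average of the two visits = (D0 + D36)/2 + (b + o)/2.

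So b enters the baseline contrast in full, the interaction in full with opposite sign, and the average by half. These are the only two of the model's three time points with both conditions: the 1-month visit is tested without the device only, so 5 of the 2 × 3 = 6 cells are filled.

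**3. Illustration (assumed shifts).** Take D0 = 0 and a paired t-test at two-sided 5% (assumed). Let δ be b divided by the SD of the paired differences. The rejection probability is that of a noncentral t with n − 1 degrees of freedom and noncentrality δ√n. The exoskeleton group has n = 10. If the expected 12 completers of 15 are lost proportionally (assumed), n = 10 × 12/15 = 8.

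| δ (assumed) | n = 10 | n = 8 |
|---|---|---|
| 0 | 5.0% | 5.0% |
| 0.2 | 8.8% | 7.8% |
| 0.3 | 13.6% | 11.4% |
| 0.5 | 29.3% | 23.2% |
| 0.8 | 61.6% | 49.6% |

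**4. What balancing order does.** Let π be an additive effect on whichever test comes second, with n1 participants tested with the device first and n2 without it first. The mean with-minus-without difference is then D + π(n2 − n1)/n. A 5/5 split gives D + 0. If dropout left 3 and 5, it gives D + π(5 − 3)/8 = D + 0.25π, which is why order should also be in the model.

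**5. Data already scheduled.** Table 2 appears to mark 5xSTS, 10mWT and 6MWT daily, and GaitRite, knee range and TUG weekly, in both conditions in the early training columns. The session-number row does not line up cleanly with the test rows, so this reading is tentative. Energy expenditure without the device has no mark in the early training columns. The with-device F-Scan row is irregular: it has a mark in the first column, where the without-device baseline sits, and none in the first mid-training assessment column, where the other with-device rows have one.

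**The case against.** The strongest reply is that Table 2 already appears to provide without-device tests in the same sessions for the primary outcome. That stands as far as data collection goes. But the text defines the without-device baseline as the pre-training test, and the analysis section does not name the daily values as comparator. For the 5xSTS the defect is therefore mainly an undefined comparator and is cheap to repair. For energy expenditure no such test is visible.

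A second reply is that some delay is unavoidable, because a person must be fitted and acclimated before being tested in the device. This is true, but it does not prevent repeating the without-device test at that same point.

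A reader might infer three stronger things, none of which the documents support:
- *That fatigue or warm-up falls wholly on one condition at later visits.* No order is fixed, and the assessment windows in Table 2 leave room for testing on separate days. A habitual order could cause bias, but the plan does not impose one.
- *That the bias flatters the device.* Practice could favour the later, with-device test. Remaining unfamiliarity with a device of about 15 lb, or fatigue within the session, could act the other way.
- *That the whole trial is confounded.* The randomised group-by-time comparison and the training effect measured without the device do not use the with-device baseline.

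**Conclusion.** The concern holds for the baseline device contrast and, through it, the condition-by-time interaction: by the plan's own rule both are confounded with practice and early training, and the model cannot separate them. At later assessments, order and rest are unspecified, which permits bias but does not show it.

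The size and net direction are unknown. The documents give no 5xSTS mean, SD or practice effect, so no bias in seconds can be stated. The rejection rates above rest on assumed shifts, an assumed 5% level and a true device effect of zero; they show only that moderate shifts would matter at this sample size. Pilot status lowers the stakes but does not make the contrast interpretable. The change is worth making because it is cheap and concerns the primary aim.

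**What to change.** 1. Keep the pre-training without-device value as baseline for the training and between-group contrasts only.
2. For the device contrast, name as comparator the without-device test from the same session as the with-device test in sessions 1–3. Confirm from the Table 2 columns that 5xSTS, 10mWT and 6MWT are scheduled this way. Schedule the weekly GaitRite, knee range and TUG tests in both conditions on the same day, since weekly marks alone do not guarantee same-session pairs.
3. Randomise exoskeleton participants, in balanced fashion, to with-first or without-first. Set a rest interval, test before that day's training, and include order in the model, because dropout may unbalance a 5/5 split.
4. For energy expenditure, either take the without-device test in the same period as the with-device baseline test, or label the baseline device contrast as confounded with time and rest the device conclusion on the session-36 pair. The second option gives up a clean baseline contrast under the secondary aim, and the plan should say so.
5. For F-Scan, first reconcile the with-device row of Table 2, then apply the same rule.

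**Cost:** revised wording and a ten-line order list. Half the exoskeleton participants would put on the device before the first test of a visit, one degree of freedom goes to order, and one energy test may have to be moved or added.

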Completers	-	0	2	3	3	3	1	-	12

Figure 4: Keeogo
Page | 7

~15lbs and consists of a combination of soft material and rigid structure that can be adjusted to the person, while attached to both legs.

The motors are attached on the shaft just above the knee and capable of providing various levels of assistance of knee extension (up to 40Nm) and of knee flexion (up to 20Nm) which can be adjusted for each leg independently. This system can assist during ambulation and during concentric and eccentric phases of functional mobility activities (i.e., sit to stand, stand to sit, squatting, lunging and stooping). The device only provides assistance as the user starts to actively perform a movement and does not completely control movement. The user is able to stop the movement, even in the middle of a gait cycle, by volitionally stopping movement of their leg. Therefore, intent to perform the movement is required which will ensure they remain active even if the effort level is diminished because of the assistance provided by the motor.

The system is powered by a lithium-ion battery that can be clipped on the waist belt, making it portable and usable in the home and community. The assistance applied to each leg can be adjusted separately and in two ways. Gross adjustments can be changed by the user at any time using the integrated control unit. The level of assistance is indicated by a colored light emitting diode. Fine tuning the assistance level is accomplished by the trainer using a tablet interface with configuration software.

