The health risks associated with this research study are considered greater than minimal risk. All the risks with this study are associated with the research being conducted and there are no therapeutic risks. As with any investigational study, there may be adverse events or side effects that are currently unknown. In the case of a serious adverse event during the study, hospital emergency personnel will be summoned by study personnel. The following list contains potential risks/and or discomfort related to study procedures:

The risk of falling: This could be caused by loss of control of the ambulation activity by the participant or therapist as well as malfunction of the Keeogo device itself. The risk of falling will be minimized by having experienced research personnel conduct the participant training sessions with assistance as needed and participants will be allowed to use their usual assistive device (cane, walker or other), if needed, when they ambulate with and without the Keeogo. The risk of falling is minimized by excluding individuals with stroke who cannot stand and ambulate.

Discomfort, skin pressure/friction, bruising, pain, or unusual swelling caused by the exoskeleton which has the potential to lead to skin breakdown or abrasions. This risk will be minimized by a thorough skin check performed by experienced research personnel at each training session. Adjustments to the device fit and additional padding will be assessed to decrease the risk of skin breakdown as well.

Blood pressure instability during use of the device related to physical activity during testing and training procedures may occur. This risk will be reduced with frequent subjective assessment of participant's symptoms as well as assessment of blood pressure and heart rate prior to training, as necessary during training and following training. Activity will be stopped in the event of instability of vital signs and as recognized by experienced research personnel. Medical clearance will be required prior to any study related activities.

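### Dividing F-Scan load by body weight alone counts the roughly 15 lb Keeogo as limb load in the with-versus-without-device comparison (about 6% relative at 250 lb, more in lighter participants)

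*Combined protocol and SAP*

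**What the plan says.** Outcome Measurements and Testing sessions defines the F-Scan measure: "This system will measure the percentage of total body weight loaded during the different segments of the stance phase". It has the gait measurements taken both with and without the device. Description of Data and Statistical Analyses repeats the denominator: the loading profile "will be normalized over the gait cycle as percentage of gait cycle and percentage of body weight for each foot". The area under each curve gives a total load per limb, and heel-strike, mid-stance and toe-off values are read from the same curve.

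The same section plans a mixed model ANOVA for "main and interaction effects of the two conditions (without [w/o] and with [W] Keeogo exoskeleton) in the experimental group".

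The Technical Description of the Keeogo puts the device at about "15lbs and consists of a combination of soft material and rigid structure that can be adjusted to the person"; it is attached to both legs. Inclusion Criteria require a weight under 250 lb and set no lower limit.

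Specific Aims makes "knee ROM and loading of the paretic LE while ambulating over ground with and without the device" part of a secondary aim, and says the device's assistance is "hypothesized to promote greater use of the paretic limb in persons with stroke". For energy expenditure, the same section predicts that the baseline comparison "will not show any metabolic changes due to the added weight of the device". No comparable allowance is made for foot load.

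**The concern.** An insole registers whatever weight passes through the foot. With the Keeogo on, that includes the Keeogo, since the documents describe no separate contact between device and ground. The numerator therefore gains about 15 lb in one condition while the denominator stays the same. A participant who walks exactly as before, with the same division of load between limbs, will show more load on both limbs when wearing the device.

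The shift has the same sign in every participant whenever any device weight reaches the feet, so averaging over about 10 people does not remove it. It falls on the main effect of condition and its post hoc t-tests, and it points the way the protocol hopes. Part of an apparent gain in paretic loading would be the weight of the equipment. Specific Aims also says the results are meant to power later studies, so an inflated device effect would carry forward into their planning.

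**Working it through.** The plan gives no figure for this effect, so there is none to reproduce.

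**Inputs from the documents.** Device weight about 15 lb (Technical Description of the Keeogo); body weight under 250 lb (Inclusion Criteria); denominator is body weight only (Outcome Measurements and Testing sessions; Description of Data and Statistical Analyses).

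**Assumed inputs.** Body weights of 200 and 150 lb; a 40/60 paretic/non-paretic division of load; 10% of body weight through a walking aid in the sensitivity check.

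**Average effect.** In steady level walking, the vertical force averaged over a full gait cycle and summed over both feet equals the weight supported. With all weight through the feet, the sum rises from W to W + 15, a relative increase of 15/W:

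- 250 lb: 15/250 = 6.0%
- 200 lb: 15/200 = 7.5%
- 150 lb: 15/150 = 10.0%

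These are relative increases. They equal points of body weight only when summed over both feet, or when one limb carries everything.

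**Paretic limb, device weight divided as existing load.** A limb with share s reads s(W + 15)/W under the plan, and s with W + 15 as denominator. For s = 40%:

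| Body weight | Plan | Denominator W + 15 |
|---|---|---|
| 250 lb | 0.40 × 265/250 = 42.4% | 40.0% |
| 200 lb | 0.40 × 215/200 = 43.0% | 40.0% |
| 150 lb | 0.40 × 165/150 = 44.0% | 40.0% |

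**Paretic limb, device weight split evenly (7.5 lb a side).**

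| Body weight | Paretic load | Plan | Denominator W + 15 |
|---|---|---|---|
| 250 lb | 100 → 107.5 lb | 107.5/250 = 43.0% | 107.5/265 = 40.6% |
| 200 lb | 80 → 87.5 lb | 87.5/200 = 43.75% | 87.5/215 = 40.7% |
| 150 lb | 60 → 67.5 lb | 67.5/150 = 45.0% | 67.5/165 = 40.9% |

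At 200 lb the paretic reading rises by 3.75 points (3.75/40 = 9.4% relative), and the non-paretic load goes from 120 to 127.5 lb (6.25% relative). The changed denominator leaves 0.70 points, so it removes 1 − 0.70/3.75 = 81% of the artefact.

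**Walking aid.** Potential Risks says "participants will be allowed to use their usual assistive device (cane, walker or other), if needed, when they ambulate with and without the Keeogo". At 200 lb with 20 lb through the aid, the feet carry 180 lb without the device. The relative inflation is then:

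- all device weight through the feet: 15/180 = 8.3%
- device weight divided as existing load: (15 × 0.9)/180 = 7.5%
- half the device weight through the aid: 7.5/180 = 4.2%

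The changed denominator is also imperfect here. In the last case the two feet together read 187.5/215 = 87.2%, against 180/200 = 90.0% without the device, so it over-corrects by 2.8 points.

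**The case against.** The strongest reply is that the extra load is real. The limb does bear the device, and percentage of body weight is a fair measure of load borne, which suits the protocol's interest in preserving bone and muscle. That stands, and it is a reason to keep the measure. But the hypothesis concerns greater use of the paretic limb, and load added by the equipment does not show that.

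Second, the reach is narrow. A nearly constant offset largely cancels from the effect of time and from the condition-by-time interaction, which bears most directly on the training question. The 1-month follow-up is done without the device, and the between-group comparison can rest on device-free readings. This is correct and limits the harm to the main effect of condition and its post hoc tests.

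Third, Specific Aims asks whether load becomes more symmetrical, and a between-limb ratio that largely cancels the offset can be formed from the planned data. However, that question is assigned to the instrumented carpet, and the analysis section defines no F-Scan ratio.

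Fourth, an even split of device weight may overstate the paretic effect. In single support the stance limb carries the whole device, and the protocol itself says the paretic limb takes less weight and time. Proportional sharing, giving 3.0 rather than 3.75 points at 200 lb, may be closer.

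Two uncertainties remain. The documents give no F-Scan variability or important difference, so it cannot be shown that a shift of this size would change a conclusion. They also do not say how or when body weight is taken. Weight without the device is the natural reading, and if weight with it on was intended, one clause would settle the matter.

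**Conclusion.** The concern holds. Followed as written, the plan biases one contrast on a secondary aim, exoskeleton-group limb load with versus without the Keeogo, towards the hypothesised benefit. The average relative inflation is about 6.0% at the 250 lb limit and larger below it, for example 7.5% at 200 lb and 10.0% at 150 lb.

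This assumes that the device weight reaches the ground through the feet in proportion to existing load. If a cane or walker takes a larger part of it, the inflation is smaller (4.2% in the example) but still positive. Heel-strike and toe-off peaks need not scale exactly with added mass, so the figures fit the area under the curve best. The primary 5xSTS aim, the device-free comparisons and the 1-month follow-up are untouched, and change over time within one condition is nearly so. It should be corrected before analysis, but it does not threaten the trial's main result.

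**What to change.** In Description of Data and Statistical Analyses, for the with/without contrast:

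- Divide with-device F-Scan load by body weight plus worn device weight, or by weight measured with the device on. Divide device-free load by body weight.
- Report the paretic share, paretic/(paretic + non-paretic), alongside it.
- State that both remove the artefact fully only if device weight divides between the limbs as existing load does.
- Keep percentage of body weight as a report of absolute load borne and for comparisons within one condition.
- Record whether a cane or walker was used in each F-Scan test. This helps interpretation and is not essential to the correction.

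The cost is one changed denominator, one derived variable and a note of aid use, with no new measurement beyond the device weight. The apparent device effect in this contrast will be somewhat smaller.
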